## VERSION NUMBER/DATE:

## REVISION HISTORY

Revision #	Version Date	Summary of Changes	Consent Change?
0	10.10.19	Resubmission into new RAMP template, Study Design Changes, names based reporting to DOH,	YES
1.0	4.27.20	Adding that those in Cohort 1 can participate in Qual interview, Long chain referral. We will administer a consent addendum for Cohort 1 participants.	New consent addendum
2.0	9.24.20	Update Study procedures for COVID, Remote study procedures, remote HIV/ STI Testing options, Information sheet for existing appointments with enrolled participants for COVID.	

## 1.0 Study Summary

Study Title	Comparative effectiveness trial of clinic-based delivery of an HIV risk reduction intervention (YMHP) for YMSM, Phase 2
Study Design	Comparative Effectiveness Trial (CET), Randomized Control trial (RCT)
Primary Objective	The purpose of this study is to adapt and test the effectiveness of the Young Men's Health Project (YMHP) at three subject recruitment venues (SRVs) within the Adolescent Medicine Trials Network for HIV/AIDS Interventions (ATN), in an effort to reduce HIV and STI disparities among urban young men who have sex with men (YMSM). We will conduct a comparative effectiveness trial to compare the effectiveness of the YMHP intervention delivered via two modalities – clinic-based versus remote delivery – following HIV counseling and testing (HIV C&T).
Secondary Objective(s)	To examine differences in effectiveness and cost by method of delivery, and to use our observations about the implementation of YMHP to improve portability and scalability. The study will also help us better understand HIV-prevention focused self-management behaviors among HIV-negative YMSM.
Research Intervention(s)	We are comparing two modalities for the delivery of the YMHP – clinic-based versus remote. YMHP consists of four sessions during which youth choose which particular behaviors (sexual risk or substance use) to discuss. The community health work (CHW) elicits the client's view of the problem using standard motivational interviewing (MI) techniques, building motivation for change by eliciting and reinforcing change talk and clarifying the youth's own personal priorities (through a structured values card sort activity). The CHW will discuss options for a behavior change plan, and, if the client is willing to proceed, the client sets goals. Starting 10/15/19- comparing YMHP (participants chooses modality for delivery as clinic-based or remote) versus HIV testing and counseling standard of care.
Study Population	Adolescent age (15-24 years) HIV-negative YMSM
Sample Size	Phase 2 N = 180
Study Duration for individual participants	Phase 2: 15 months, Starting 10/15/19- 12 months
Study Specific Abbreviations/ Definitions	Adolescent Medicine Trials Network (ATN) Condomless anal sex (CAS) Comparative Effectiveness Trial (CET) Community health worker (CHW) HIV counseling and testing (HIV C&T) Motivational interviewing (MI)

PROTOCOL TITLE: Comparative effectiveness trial of clinic-based delivery of an HIV risk reduction intervention (YMHP) for YMSM, Phase 2

	Subject recruitment venue (SRV) Sexually transmitted infection (STI) Young Men's Health Project (YMHP) Young men who have sex with men (YMSM)
--	--

## 2.0 Objectives

Aims: In collaboration with three subject recruitment venues (SRVs) in the Adolescent Medicine Trials Network or HIV/AIDS Interventions (ATN), *Scale It Up (SIU)*, our goals are to better understand HIV-prevention focused self-management behaviors among HIV-negative YMSM, and to study the implementation of YMHP to improve the portability and scalability. Our CET design gathers information about implementation. In a “Hybrid 2” trial, the dual goals are to determine which treatments work in which settings and to simultaneously answer implementation science questions about the potential barriers/facilitators to a treatment’s widespread and sustained implementation. The SRVs will help the study assess and address practical problems at the frontline of service provision to pave the way for a comprehensive program to reduce HIV infection among YMSM that reflects the complexities of real-world adolescent HIV clinics.

Aim 1: Adapt YMHP for clinic and remote delivery (via phone or video chat) by existing HIV clinic staff, CHWs, who work with YMSM aged 15-24. We will consult with staff to obtain input on how best to implement YMHP to maximize feasibility, acceptability, and sustainability. This input will also identify issues with adapting YMHP for delivery for YMSM aged 15-18, and for remote delivery.

Aim 2: Assess the effectiveness of YMHP when delivered in a real world setting compared to a treatment as usual control – individual HIV testing – which represents a common standard of care.

Aim 2a: Assess the cost effectiveness of both delivery formats of YMHP to enhance the likelihood of uptake of this best evidence intervention.

Aim 2b: Assess the five components of the self-management model and how these components vary over time, are directly improved by the interventions, and mediate intervention effects.

Aim 3: Test a sustainable model of YMHP implementation in real world adolescent clinics. We will utilize local supervisors within the clinic setting to sustain the CHWs fidelity to delivering the MI-based YMHP intervention. We will monitor fidelity throughout the trial and conduct assessments and qualitative interviews with key stakeholders to determine the barriers and facilitators of YMHP implementation utilizing the *SIU Exploration, Preparation, Implementation, Sustainment (EPIS)* model (see ATN 153 EPIS Study Procedure Guide).

Secondary Aim: The design will result in a subsample of youth who were randomized to receive YMHP in a clinic-based or remote delivery. It will also yield a subsample who are allowed to self-select delivery method. We will utilize these subsamples to assess youth preferences for

PROTOCOL TITLE: Comparative effectiveness trial of clinic-based delivery of an HIV risk reduction intervention (YMHP) for YMSM, Phase 2

delivery format, evaluate whether delivery format is associated with session retention, and test for any indications that delivery format is associated with response to intervention.

We will achieve our aims over 2 phases of the study.

Phase 1: We conducted focus groups with youth as part of our formative research to obtain implementation feedback about the delivery of the YMHP intervention and intervention components to ensure culturally competent, feasible, and scalable implementation both in the clinic setting and via remote delivery. Feedback from these focus groups at the 3 SRVs has been used to modify the YMHP intervention prior to the launch of Phase 1. Phase 1 focus groups were conducted with youth at each of the 3 SRVs to gather information that would be used to better implement YMHP. Groups were broken down into two age groups, 15-17 and 18-24.

We will train a minimum of 2 CHWs at each SRV to deliver the YMHP sessions, who must demonstrate competence according to the Motivational Interviewing Treatment Integrity (MITI) before providing the intervention in Phase 2.

Phase 2: We will recruit and enroll 270 YMSM, aged 15-24, 90 at each of the 3 SRVs. Enrollment will be limited to HIV-negative YMSM who report recent substance use and either CAS or a positive STI test result. Participants will be randomized to receive a standard of care enhanced HIV testing and counseling versus the YMHP intervention in person or by remote delivery (initial in-person session). The modality of delivery is chosen by the participant and involves completion of the 4 YMHP sessions and the delivery of pre-exposure prophylaxis (PrEP) information and navigation services to interested participants. Fidelity will be monitored throughout the trial. Sessions will be audio-recorded for MITI fidelity coding, and CHWs and supervisors will be given implementation support throughout the study period.

The current application is for Phase 2; Phase 1 has already been complete.

Hypothesis: The primary hypothesis is that receipt of YMHP (regardless of delivery format) will be associated with greater improvements in sexual health management (as measured by decreased STIs, CAS, and increased PrEP uptake/adherence) as well as reductions in substance use, compared with youth who receive the standard of care (individual HIV testing) only.

Secondary Hypothesis: We hypothesize that youth who elect to receive YMHP remotely will report more barriers to accessing health care compared to those who elect to receive the intervention in clinic. In addition, we hypothesize that remote-based YMHP will demonstrate greater improvements in sexual health management (as measured by decreased STIs, CAS, and increased PrEP uptake/adherence) as well as reductions in substance use, compared with clinic-based YMHP, among YMSM who do report barriers to health care access. In contrast, it is hypothesized that clinic-based YMHP will demonstrate greater improvements in sexual health management and reduced substance use among YMSM who do not report barriers to health care access.

PROTOCOL TITLE: Comparative effectiveness trial of clinic-based delivery of an HIV risk reduction intervention (YMHP) for YMSM, Phase 2

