## 10.0 Subject Population

### Inclusion Criteria

Individuals who express interest in YMHP must demonstrate the following criteria to be enrolled in the study:

- HIV-negative test result from the past 90 days
- 15-24 years of age
- Currently identifying as male (regardless of sex assigned at birth)
- Sex with men in the past 90 days
- Self-report  $\geq 3$  days of substance use\* (drugs or heavy drinking) in the past 90 days
- Self-report  $\geq 1$  episode of condomless anal sex (CAS) in the past 90 days, or a positive STI test result in the past 90 days
- Living in the Detroit, Miami, or Philadelphia metropolitan areas
- Able to communicate in English

\*substance use includes: heavy drinking (5+ drinks on one occasion), marijuana, crack, cocaine, MDMA, opiates (less than 5 days IDU), ketamine, GHB, meth, prescription drugs for fun, sedatives, amphetamines, and hallucinogens

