1.2 Quantitative Analysis Plan

The primary hypothesis is that receipt of YMHP (regardless of delivery format) will be associated with greater improvements in sexual health management (as measured by decreased STIs, CAS and increased PrEP uptake/adherence) as well as greater reductions in substance use, compared with youth who receive the standard of care (individual HIV testing) only. Our secondary hypothesis is that youth who elect to receive YMHP remotely will report more barriers to accessing health care compared to those who elect to receive the intervention in clinic. In addition, we hypothesize that remote-based YMHP will demonstrate greater improvements in sexual health management (as measured by decreased STIs, CAS, and increased PrEP uptake/adherence) as well as reductions in substance use, compared to clinic-based YMHP, among YMSM who do report barriers to health care access. In contrast, it is hypothesized that clinic-based YMHP will demonstrate greater improvements in sexual health management and reduced substance use among YMSM who do not report barriers to health care access. Self-management model analysis is described in the AC.

The AC will test the effect of clinic-based versus remote delivery on STI rates, alcohol and drug use behavior, CAS, and PrEP uptake through multi-level growth mixture modeling (GMM). A separate model will be run for each outcome. Each model will be a 2-level model in which individuals (Level I) are nested in clinics (Level II). This approach controls for the non-independence of individuals within clinics. Because three SRVs provide extremely limited predictive power at Level II, no site covariates are included in the model. (The models are empty at Level II).

In a GMM, a latent growth curve with an intercept and linear slope factor is specified. Latent class analysis is applied to these 2 growth components (intercept and slope) to identify groups of individuals who share trajectories. For example, with regard to drug or alcohol use, “immediate and sustained responders” may have the lowest post-intervention intercept and a flat slope. Meanwhile, “non-responders” might have the highest post-intervention intercept and a flat slope. In contrast, “delayed responders” might have a high post-intervention intercept but a significant negative slope, indicating reductions in missed medication over the follow up period.

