If modeling results indicate that discrete classes are not present, we will proceed with analyses in which the growth factors (intercept and slope) are predicted directly by intervention condition (and demographic factors found to be associated with condition after randomization or with attrition over follow up). GMMs can subsequently incorporate predictors of class membership. These analyses can be conceptualized as a multi-nominal logistic regression with the latent trajectory-class membership constituting the outcome. The predictors

of primary interest will be intervention condition, the presence of any barriers to health care access, and the interaction between condition and barriers to access. We will include as covariates any demographic variables that were associated with condition after randomization or with attrition over the follow up period.

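### The outcome models carry no baseline value of the outcome, so participants who reported no heavy drinking, drug use or CAS at entry can be classed with those who stopped

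*Protocol*

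**What the plan says.** Entry is either/or on both risk criteria. Protocol 2.0 (Phase 2) says: "Enrollment will be limited to HIV-negative YMSM who report recent substance use and either CAS or a positive STI test result". Section 10.0 requires at least 3 days of substance use, which it glosses as "drugs or heavy drinking) in the past 90 days". It also requires at least one "episode of condomless anal sex (CAS) in the past 90 days, or a positive STI test result in the past 90 days".

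SAP 1.2 then says: "A separate model will be run for each outcome". It does not restrict any model to participants who had the behaviour at entry. On how classes are formed: "Latent class analysis is applied to these 2 growth components (intercept and slope) to identify groups of individuals who share trajectories". As an example for drug or alcohol use, it says that immediate and sustained responders "may have the lowest post-intervention intercept and a flat slope".

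On the test of condition: "GMMs can subsequently incorporate predictors of class membership". Class membership becomes the outcome of a multinomial regression on condition, barriers to care and their interaction. On adjustment: "We will include as covariates any demographic variables that were associated with condition after randomization or with attrition over the follow up period". If no discrete classes are found, condition predicts the intercept and slope directly, with the same kind of demographic covariates.

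**The concern.** The primary hypothesis is about improvement and reduction. A level seen only after the intervention does not show change. If the baseline value lies outside both the trajectory and the covariates, the lowest class on heavy drinking can hold two kinds of participant: those who cut down to nothing, and those who reported none on entry. The second kind appears in both arms whatever YMHP does. The contrast between arms is then diluted, and the reported share of responders does not answer what fraction of drinkers, drug users or youth with CAS changed. The same holds for drug use and CAS. It does not hold for PrEP uptake: Protocol 10.0 excludes current users of Truvada as PrEP, and success there is an increase.

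**Working it through.** **1. Who can enter without the behaviour.** From Protocol 10.0, marijuana use alone meets the substance criterion without heavy drinking, and heavy drinking alone meets it without drug use. A positive STI test meets the sexual-risk criterion without CAS.

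**2. What the classes can see.** Take participant A with 0 heavy-drinking days before and after. Take participant B with 8 days per 30 before (within the 7 to 9 assumed in SAP 1.2.1) and 0 after. On post-intervention data both have intercept 0 and slope 0. A flat slope in someone who improved at once implies that baseline is not on the curve; otherwise B's slope would be negative.

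**3. Whether baseline behaviour enters elsewhere.** SAP 1.2 names demographic covariates. SAP 1.2.3 tests baseline outcomes for balance but carries forward demographic factors. SAP 1.2.2 admits behavioural predictors only if attrition is differential. None is a standing term.

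**4. The plan's own figures.** SAP 1.2.1 gives no power for a class-membership test. For the counts it uses two Poisson means and claims detectable reductions of 3% (heavy drinking, 7–9 days), 4% (drug use, 3–5 days) and 5% (CAS, 2–4 acts). Solving λr = (1.96 + 0.84)·√[λ(2 − r)/135] gives 11.1–12.5%, 14.7–18.7% and 16.3–22.7%, so they do not reproduce with one 30-day count per person. That is a separate matter, and this point does not rest on those figures. What matters here is that a simple Poisson model has no room for an excess of zeros.

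**5. Illustration of dilution.** Assumptions, none of them from the documents:
- true response 30% in control and 50% in YMHP among those with the behaviour;
- a share *a* in each arm without it, all placed in the favourable class;
- 1:1 allocation of N = 270, so 135 per arm;
- two-sided 5% test of two proportions.

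Observed proportions: p0 = a + (1 − a)·0.30 and p1 = a + (1 − a)·0.50. Power = Φ[(d − 1.96·SE0)/SE1], where d = p1 − p0 and SE0 and SE1 are the pooled and unpooled standard errors.

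At a = 0.20, all participants: p0 = 0.44, p1 = 0.60, OR = (0.60/0.40)/(0.44/0.56) = 1.91. SE0 = √(0.52·0.48·2/135) = 0.0608 and SE1 = √[(0.2464 + 0.24)/135] = 0.0600. Power = Φ[(0.16 − 0.1192)/0.0600] = Φ(0.68) = 75%.

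Baseline-positive set, 108 per arm: SE0 = √(0.24·2/108) = 0.0667 and SE1 = √[(0.21 + 0.25)/108] = 0.0653. Power = Φ[(0.20 − 0.1307)/0.0653] = Φ(1.06) = 86%.

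| Share a | p0 vs p1, all | OR, all | Power, all | Power, baseline-positive (OR 2.33) | Baseline-negative among favourable class, arms pooled |
|---|---|---|---|---|---|
| 5% | 33.5 vs 52.5% | 2.19 | 89% | 91% | 11.6% |
| 10% | 37 vs 55% | 2.08 | 85% | 89% | 21.7% |
| 20% | 44 vs 60% | 1.91 | 75% | 86% | 38.5% |
| 40% | 58 vs 70% | 1.69 | 54% | 74% | 62.5% |

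The last column is 2a/(p0 + p1). With 90 per arm (the N of 180 in Protocol 1.0), power is 58% versus 69% at a = 20% and 39% versus 57% at a = 40%.

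**6. Where CAS probably sits.** Without recent CAS, entry needs a positive STI test. The SAP's only STI figure is a prevalence of .05 to .15, assumed for the remote arm. If positivity among entrants were similar (an assumption), at most 5–15% would lack CAS. At 15% the OR is 1.99 and power is 80% versus 88%.

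**The case against.** **The responder shape is only an example.** This stands. A reader might infer that the SAP defines response as the lowest level after the intervention. It does not: the wording is tentative, concerns drug or alcohol use, and the classes are estimated from the data. No responder class is described for CAS. Still, on intercept and slope after the intervention no class solution can separate stable zeros from those who dropped to zero.

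**The calculation is not the planned test.** This also stands. The plan is a multinomial model with an interaction, or growth factors regressed on condition. The two-proportion figures show direction and rough scale. They put every baseline-negative participant in the favourable class and give YMHP no preventive effect, which maximises dilution.

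**These participants can change.** A reader might infer that they never had the behaviour and cannot respond. The criteria cover 90 days of self-report, and participants aged 15–24 are followed for about 12 months. They can start or resume, which is a reason to keep them in an all-randomised analysis.

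**Responders need not be mostly non-users.** At a 20% share they make up 38.5% of the favourable class over both arms, so that inference fails at low shares.

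**Substance use may be one outcome.** SAP 1.2 lists alcohol and drug use as a single item, and every entrant has at least 3 substance-use days, so nobody would be at zero on a composite. SAP 1.2.1, however, powers heavy drinking and drug use separately. The SAP should say which is meant.

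**Analysing everyone is legitimate.** Aim 2 is effectiveness in a real-world setting, and randomisation balances baseline-negative participants on average. The documents do not support a claim of inflated type I error, nor a claim that the restricted set must be the main test.

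**Conclusion.** The concern holds in a limited form. For heavy drinking, drug use and CAS, the SAP has no standing term for the baseline value and no rule for participants who reported none. Its example class would tend to merge them with participants who stopped. The consequences are dilution of the condition effect, lost power and a misleading responder share. If no classes emerge, the label disappears but the fallback model still omits baseline behaviour, so dilution can remain.

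The size cannot be taken from the documents. Under the stated assumptions the power loss against the baseline-positive set runs from 2 points at a 5% share to 20 points at 40%, with CAS probably at the low end. The reading also assumes that the growth curve starts after the intervention, as the SAP's example implies. This should be corrected, but it does not invalidate the trial.

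**What to change.** In SAP 1.2, for heavy drinking, drug use and CAS:

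- Keep the all-randomised analysis, and include the baseline value of the outcome in its model, in the fallback model as well.
- If the growth mixture model is kept, treat none reported at baseline as a known class that is not counted as response. A baseline covariate alone would not mend the label, because the outcome category would still mix no behaviour with stopping.
- Report beside it the condition effect among participants who reported the behaviour at the pre-randomisation baseline. State the expected number in that set next to the power for that outcome.
- Say whether alcohol and drug use are separate outcomes, and which time points define the intercept.

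Protocol 6.0 places randomisation after the baseline CASI, so the baseline-positive comparison stays randomised. For virtual baselines, confirm that the CASI was completed before allocation. The cost is SAP wording and one further analysis per outcome on data already collected. The downside is a smaller n in that set and a less favourable stated N for those outcomes.

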### **3.0 Background**

Young (aged 16-24) men who have sex with men (YMSM) are disproportionately at risk for human immunodeficiency virus (HIV) and sexually transmitted infections (STIs). While new HIV infection have fallen or remained stable among other groups, YMSM have experienced a 132% increase in new infections since 2002. From 2008-2011, YMSM aged 13-24 had the greatest percentage increase (22%) in new HIV infections. YMSM of color are especially at risk: in 2011, among YMSM aged 13-24 with HIV infection, 58% were Black and 20% were Latino.

Young males aged 15-24 are vastly overrepresented in rates of STIs. In 2013, 15-24 year old males accounted for more than half (57%) of all male cases of Chlamydia trachomatis (CT) infection and 46% of Neisseria gonorrhoea (GC). Young men aged 20–24 had the highest rate of syphilis from 2008-2012. Further, sexual orientation disparities exist – e.g., men who have sex with men (MSM) accounted for 75% of all syphilis cases in 2013. Ethnic and racial disparities exist in the incidence of other STIs among YMSM. Young Black men aged 15-24 have a rate of CT infection 5.5-9.5 times higher and GC rates 10.4-13.0 times higher than White men. A recent study of HIV-negative MSM diagnosed with rectal CT/GC at STI clinics between 2008-2010 showed that such infections greatly increase HIV incidence. In 2013, MSM accounted for 3 quarters of all primary and secondary syphilis cases diagnosed in the US – an increase of 10% since 2012.

Rates of HIV diagnoses also vary geographically across the US, with urban areas disproportionately affected. Detroit, Philadelphia, and Miami are geographically diverse cities that have high rates of HIV and STIs among MSM and communities of color. The US Preventive Services Task Force and CDC recommend screening sexually active MSM at least annually, and potentially every 3 or 6 months for MSM at higher risk of HIV infection. CDC also recognizes the need for targeted outreach and screening for YMSM of color in non-healthcare settings and accordingly funds CBOs to serve this population through targeted promotion, testing and navigation to continuum of HIV prevention services. This underlines the need to study implementation of the YMHP intervention, for its significant public health potential in tackling HIV/STI disparities among urban YMSM by reducing risk behaviors associated with HIV infection, as part of a continuum of effective prevention services for this population.

